2.3 Potential Risks and Benefits

2.3.1 Known Potential Risks

Safety and efficacy has been established for pediatric patients 6 months of age or older. Ivermectin 0.5% lotion is not recommended for patients under 6 months of age due to the increased risk of systemic absorption, given a high ratio of skin surface area to body mass.

The following reactions, reported in less than 1% of subjects treated with Ivermectin 0.5% lotion include:

- Conjunctivitis
- Ocular hyperemia
- Eye irritation
- Dandruff
- Dry skin
- Skin burning sensation

In the case of accidental or significant exposure, the following adverse effects have been reported most frequently:

- Rash
- Edema
- Headache
- Dizziness
- Asthenia
- Nausea
- Vomiting
- Diarrhea

Other adverse effects that have been reported include:

- Seizure
- Ataxia
- Dyspnea
- Abdominal pain
- Paresthesia
- Urticaria
- Contact dermatitis

A theoretical concern exists about medication errors that might result in the ingestion of the ivermectin product (particularly in young children), therefore it should only be administered under the direct supervision of an adult.

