7.1 Study Procedures/Evaluations

Basic demographic information, including date of birth, sex, ethnicity, and race will be recorded at the Screening Visit.

Medical history will be collected at the Screening and Baseline Visits. Relevant medical history, alcohol and tobacco history, and past history of head lice will be documented.

All medications (both prescription and nonprescription, including vitamins, herbals, topical, inhaled, and intranasal) taken within 30 days prior to the start of the Study Drug and through the final study visit will be recorded on the appropriate eCRF (using their generic and brand names, if known) with the corresponding indication, start and stop dates. At each study visit, subjects will be asked whether they have started or discontinued any medication since their previous study visit. This includes single use or PRN (as needed) medication use.

Vital signs will be collected at Baseline Visit 1 and Final Study Visit 5. Vital signs will include body temperature, heart rate and blood pressure (systolic and diastolic). Blood pressure and pulse rate will be measured after the subject has been sitting restfully for at least 5 minutes. Any abnormal characteristics of vital signs will be evaluated by the Investigator based on

Protocol Number: MAP-7189

Version 1.3; 28 December 2017

their significance. Any abnormal vital signs will be considered AEs if they require therapeutic medical intervention, and/or if the Investigator considers them to be AEs based on his/her clinical judgement.

Physical examination, including height, weight, and evaluation of organs and systems (General Appearance, Heart/Cardiovascular, Lungs, Gastrointestinal, Ears / Nose / Throat, Extremities, and Skin) will be assessed at the Screening Visit.

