7.1.1 Study Specific Procedures

In addition to the regular standard of clinical care, the following study specific procedures will be included as part of the study.

Past medical history of and previous treatment of head lice must be recorded irrespective of the term it was given. Corresponding condition shall be captured in the subject's Medical History.

Visual Assessment of Head Lice:

Subjects and their household members will be thoroughly assessed for a minimum of 15 minutes for the presence or absence of live head lice, including adult lice, nymphs, and nits. Results will be recorded on the Site Assessment form.

Skin/Scalp Irritation Assessment:

Subjects will be assessed for skin and scalp pruritus, erythema, excoriation, and pyoderma. Results will be recorded on the Site Assessment form.

Ocular Irritation:

Subjects will be assessed for eye irritation, conjunctivitis, and ocular hyperemia. Results will be recorded on the Site Assessment form.

Subject Diary:

Administration of a checklist for laundry disinfection measures, application and removal of the study drug for index subject. Subject Assessments:

Administration of questionnaires for subject-reported outcomes. The site will provide a Subject Self-Assessment Worksheet to record the grading of Itching and Stinging/Burning sensations. Analysis of tolerability will be based on scoring scales of Stinging/Burning and Itching sensations collected during Subject Self-Assessment at all follow-up visits between the test and reference treatment groups.

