7.3.2 Enrollment/Baseline

Enrollment/Baseline Visit Day 1 (Visit 1/ Visit 2)

- Review concomitant and prohibited medications.
- Record vital signs, results of examinations, other assessments.
- Perform assessment for living head lice on index subject and household members (up to 3 per household) for visual confirmation of infestation for a minimum of 15 minutes.
- Provide Standard of Care treatment on-site to infested household members (up to 3 per household).
- Randomize the index subject.
- Provide the study treatment for index subject.
- Provide index subject with subject diary and homecare instructions.
- Record Subject Self-Assessment for index subjects.
- Inform index subject when to come back for their first follow-up visit.

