7.3.3 Follow-up

Follow-up Visit Day 2 (Visit 3) (+/- 1 Day)

- Record adverse events as reported by participant or observed by investigator.
- Collect used test tube product from index subject.
- Concomitant and prohibited medication review.
- Perform assessment for living head lice on index subject for visual confirmation of infestation for a minimum of 15 minutes.
- If active lice are present on index subject, provide Standard of Care and withdraw the subject from the study.
- Record Subject Self-Assessment for index subjects.
- Perform skin/scalp irritation and ocular irritation for index subjects and record results on Site Assessment form.
- Record index subject's adherence to treatment program through collection of subject diary.
- Inform index subject when to come back for their follow-up visit.

Follow-up Visit Day 8 (Visit 4) (+/- 2 day)

- Record adverse events as reported by participant or observed by investigator.
- Concomitant and prohibited medication review.
- Perform assessment for living head lice on index subject for visual confirmation of infestation for a minimum
 of 15 minutes.
- If active lice are present, provide Standard of Care and withdraw the subject from the study.
- Record Subject Self-Assessment for index subjects.
- Perform skin/scalp irritation and ocular irritation for index subjects and record results on Site Assessment form.
- Inform index subject when to come back for their final study visit.

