5.3. Tolerability Assessment

Subjects' self-assessment of itching and stinging/ burning sensations during screening and treatment periods (Visits 2 through 5), skin/scalp irritation assessment by clinical site personnel (Visits 2 through 5), and ocular irritation assessment (Visits 3 through 5) by clinical site personnel will used to assess tolerability to the study treatments. Itching is defined as intense, distracting irritation or tickling sensation in the last 24 hours and is evaluated on a scale from 0 (No Itching) to 3 (Severe Itch). Stinging/ burning is defined as sensation of the skin is painfully hot or noticeable tingling sensation in the last 24 hours and is evaluated on a scale from 0 (Absent) to 3 (Severe). Skin/Scalp irritation is evaluated on a scale from 0 (None) to 3 (Severe) for four types of irritation including Pruritus= Itching, Erythema= Redness of the scalp, Excoriation= Breaking of the skin, usually caused by scratching, Pyoderma= Sores filled with clear fluid, pus or crusting. Each type of irritation is evaluated separately and its total score is recorded. Ocular irritation is evaluated for the presence of eye irritation, Conjunctivitis, and Ocular Hyperemia on a scale from 0 (No) to 1 (Yes).

Descriptive statistics using categorical methods will be used to compare tolerability measures between the test and reference treatment groups and various study days (e.g. Baseline (Visit 2), Visit 3, Visit 4, and Visit 5). Tolerability analyses will be presented for mITT and PP populations.

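### No structured eye assessment is scheduled before treatment, so the by-visit ocular tables cannot separate new findings from pre-existing ones that persist to Day 2 or later.

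*SAP*

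**What the plan says.** Protocol 2.3.1 introduces its list of known reactions with the words "The following reactions, reported in less than 1% of subjects treated with Ivermectin 0.5% lotion include". The list has six entries: conjunctivitis, ocular hyperemia, eye irritation, dandruff, dry skin and skin burning sensation.

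Protocol 7.1.1 turns the three ocular entries into an assessment: "Subjects will be assessed for eye irritation, conjunctivitis, and ocular hyperemia". They form item 3 of the Site Assessment form (Protocol 16.4), each with a yes and a no box.

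**Timing.** SAP 5.3 places the "ocular irritation assessment (Visits 3 through 5) by clinical site personnel". The schedules in Protocol 16.1 and SAP Table 1.2 mark the same three visits (Days 2, 8 and 15). In the protocol's visit lists the eyes first appear at Day 2: "Perform skin/scalp irritation and ocular irritation for index subjects and record results on Site Assessment form".

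**Before treatment.** The Screening list (Protocol 7.3.1) has no ocular item. The Baseline list (7.3.2) has only a general line: "Record vital signs, results of examinations, other assessments". The screening physical examination (7.1) covers General Appearance and Heart/Cardiovascular, then "Lungs, Gastrointestinal, Ears / Nose / Throat, Extremities, and Skin". Eyes are not named.

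**Reporting.** SAP 5.3 scores presence as 0 or 1, with no qualifier for new or worse. Tables 22-23 and Figures 9-10 summarize these scores by visit. Change-from-baseline tables are listed for itching and stinging/burning (Tables 18-19) and for skin/scalp irritation (Tables 24-25), but not for the eyes.

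**The concern.** Local tolerability of the test lotion against the reference is the secondary objective, and SAP 5.3 counts the ocular score among the measures used to assess it. With no structured pre-treatment score, a child who arrives with a red or irritated eye that is still present at Day 2 is entered as a yes under the assigned lotion. Nothing in the ocular tables or figures tells that child apart from one whose eye reacted to the product.

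The stake is how far the ocular summary can be read. The known reactions are rare, so even a small background of eye conditions can make up much of what is tabulated. Absolute rates would look higher than the product causes. The contrast between arms would be diluted, and chance differences in background cases could look like differences between lotions.

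SAP 5.3 also lists Baseline (Visit 2) among its example study days for comparing tolerability measures. No scheduled ocular data will exist for that day.

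**Working it through.** **1. Count of scheduled assessments**

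| Source | Before treatment (Visits 1-2) | After treatment (Visits 3-5) |
|---|---|---|
| Protocol 16.1 schedule | 0 | 3 |
| SAP Table 1.2 schedule | 0 | 3 |
| Protocol 7.3.1 to 7.3.4 visit lists | 0 | 3 |
| SAP 5.3 | 0 | 3 |

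All four agree. Ocular reactions among those named in Protocol 2.3.1: 3 of 6, and they are the same three items as on the form.

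**2. Group size (the only plan figure used below)**

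280 subjects at 3:3:1 gives 280 × 3/7 = 120 per active arm and 280 × 1/7 = 40 on placebo, as in Protocol 10.5. A simulation of the stated success rule (400,000 trials; cure rates 67%, 67% and 27%; PP groups of 108 nested in mITT groups of 120) gave 81.5%, consistent with the planned 80% or more. Nothing below depends on that power.

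**3. Illustration: share of positives that are pre-existing**

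Inputs:
- *b*, the proportion of children with a pre-existing ocular finding that persists to Day 2. The documents give no figure, so 1%, 2% and 5% are assumed.
- *r*, the rate of new findings, set at 1%. This is the ceiling in Protocol 2.3.1, where it can be read as applying to each listed reaction.

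Formulas, per active arm of 120: expected positives = 120 × [b + (1 − b)r]; pre-existing = 120b; new = 120(1 − b)r; pre-existing share = b / [b + (1 − b)r].

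For b = 2%: 0.02 + 0.98 × 0.01 = 0.0298; 120 × 0.0298 = 3.6; share = 0.02 / 0.0298 = 67%.

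| b (assumed) | Expected positives | Pre-existing | New | Pre-existing share |
|---|---|---|---|---|
| 1% | 2.4 | 1.2 | 1.2 | 50% |
| 2% | 3.6 | 2.4 | 1.2 | 67% |
| 5% | 7.1 | 6.0 | 1.1 | 84% |

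The share depends on *r*. If the under-1% rate applies to each of the three ocular reactions separately and they do not overlap, the any-ocular rate could approach 3%. The shares at r = 3% are then 0.01/0.0397 = 25%, 0.02/0.0494 = 40% and 0.05/0.0785 = 64%. At r = 0.5% they are 67%, 80% and 91%.

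**4. Illustration: chance imbalance**

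Take the number of pre-existing cases in each active arm as an independent Binomial(120, b), and sum the joint probabilities over pairs that differ by at least *d*.

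| b (assumed) | Difference of 3 or more | Difference of 4 or more |
|---|---|---|
| 1% | 10% | 3% |
| 2% | 24% | 10% |
| 5% | 45% | 30% |

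A pre-treatment score would let these cases be identified and set apart.

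**The case against.** The strongest reply is that baseline information on the eyes is not absent, only unstructured. Medical history is taken at Screening and Baseline. Medications from the previous 30 days, including topical ones, are recorded with their indication. The physical examination includes General Appearance. Exclusion 7 leaves the investigator discretion over any compromising condition, and inclusion 5 asks for good general health. A reader might infer that the eyes are never looked at before treatment, but the documents do not support that. What stands is narrower: nothing requires an eye check, and whatever these routes pick up would not enter Tables 22-23.

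A reader might also infer that ocular adverse events will be misattributed. The documents do not support this as a general statement. Protocol 8.3 sends events before Baseline to past medical history, the diary asks about health problems since the last visit, and causality is judged on timing and alternative etiology. SAP 5.4 names AEs as the safety variables. The difficulty for the investigator is a lack of structured evidence, and the miscount itself is confined to the ocular tolerability outputs.

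A third tempting reading is that the named rate caps true reactions at about 1 in 120 per arm. The under-1% figure can apply to each listed reaction, so the any-ocular rate could be higher. It is also a rate of reported reactions, not of findings from an active examination at each visit.

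It is also fair to say that the protocol itself (Synopsis and 7.1.1) bases tolerability analysis on itching and stinging/burning, and that only the SAP adds the ocular score. No ocular hypothesis test is planned. As an example, a split of 5 of 120 against 1 of 120 gives a two-sided Fisher p of 0.21.

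These points reduce the weight of the matter. They do not give the ocular tables a baseline.

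**Conclusion.** The point holds as a limited design gap. Followed exactly, the plan produces ocular tables and figures that cannot separate new findings from pre-existing ones that persist to Day 2 or later.

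A reader might conclude that the Test versus Reference comparison is biased. It is not: allocation is randomized and assessment blinded, so pre-existing findings balance on average. The effect is inflated absolute rates, a diluted contrast and chance imbalance in a descriptive summary. The primary endpoint, sample size, alpha and power are untouched.

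The size is uncertain because it rests on an assumed prevalence of 1% to 5%, on those findings persisting to Day 2, and on a new-finding rate of 1%. Under those assumptions half to five-sixths of Day 2 positives would be pre-existing. With a new-finding rate near 3% the range falls to about a quarter to two-thirds. This is a worthwhile, inexpensive improvement and not a threat to the trial's conclusions.

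**What to change.** - Complete the three ocular boxes of the Site Assessment form at Visit 2, before the study drug is dispensed. Protocol 7.1.1 already records the lice assessment on that form, and 7.3.2 schedules that assessment at Baseline.
- Add an X for the ocular assessment at Visit 2 in Protocol 16.1 and SAP Table 1.2, add a line to Protocol 7.3.2, and change the ocular visits in SAP 5.3 to Visits 2 through 5.
- In Tables 22-23, show a baseline-by-visit shift (new, persisting, resolved) beside all findings. Counting only findings absent at baseline would drop children with a baseline yes. Because the score is binary, the shift will still not show worsening in a child who stays at yes, and a footnote should say so.

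**Cost.** About a minute per subject and slightly longer tables. No extra visit or staff is needed.

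**Separate item to reconcile.** SAP 5.3 gives the skin/scalp assessment from Visit 2, and Tables 24-25 need that baseline, but both schedules mark it only from Visit 3. Resolving that would not by itself create an ocular baseline.

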The primary efficacy endpoint is the proportion of index subjects who are lice free (defined as no live lice, adults or nymphs) 14 days (Day 15) after treatment. The superiority of Test and Reference treatment's cure proportions over that of the placebo will be evaluated using continuity-corrected Z-tests (α = 0.05, 2-sided). The comparability of the Test and Reference treatments will be evaluated using a 90% continuity-corrected confidence interval on the difference between their cure proportions and a bioequivalence margin = 0.20 (20%).

Secondary Efficacy Endpoint

The secondary efficacy endpoint is the number and percentage of all index subjects who are lice free at Day 2.

SAFETY ANALYSIS

Descriptive statistics on the severity and duration of adverse events (AEs) from all subjects will be determined for each treatment group for any AE that occurs in at least 5% of the subjects.

Analysis of tolerability will be based on scores of Stinging/Burning and Itching sensations collected during Subject Self-Assessment and Site Assessment at all follow-up visits between the test and reference treatment groups.

1 Key Roles

PRINCIPAL CONTACTS

CLINICAL PROTOCOL AND CONDUCT INQUIRIES

[name], M.Pharm., Ph.D.

Senior Director, Clinical Pharmacology

Mayne Pharma Inc.

email: [contact]

[name],

[name] [contact] [contact]

[name], J.D.

Project Director Biorasi LLC

email: [contact] [name] [contact]

CLINICAL SAFETY INQUIRIES

[name]

Medical Monitor

Biorasi Safety and Pharmacovigilance email: [contact] [name]

[contact]

REPORTING OF SERIOUS ADVERSE EVENTS (SAES), PROTOCOL DEVIATIONS

Biorasi Safety and Pharmacovigilance

email: [contact] [name] [contact]

2 Study Introduction

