2. OBJECTIVES

The primary objective of this study is:

- To establish the efficacy of a single application of Ivermectin 0.5% lotion in the treatment of head lice (Pediculus humanus capitis) under at-home conditions compared with Sklice® 0.5% lotion
- To demonstrate that both active lotions have superior efficacy compared to Placebo

The secondary objective of this study is:

• To demonstrate comparative safety and local tolerability of Ivermectin 0.5% lotion (Mayne Pharma, LLC) vs Sklice® 0.5% lotion.

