4. ANALYSIS POPULATIONS

The populations defined for analysis will include the modified intent-to-treat (mITT), per-protocol (PP), and the safety population.

Safety Population includes all subjects who were randomized and dispensed treatment. This is the population that will be used for the safety assessments.

Modified Intent-to-Treat (mITT) Population includes all Index subjects who met all inclusion/exclusion criteria, were randomized, dispensed treatment, and had at least one post-treatment efficacy evaluation. This is the primary population for determination of the superiority of the active treatments over placebo.

Per-Protocol (PP) Population includes all mITT subjects who applied their dispensed treatment, had no protocol deviations which could have interfered with the accurate assessment of treatment efficacy, and returned for the Day 15 visit within the allowed window. This is the primary population for the efficacy comparisons between the two active treatment groups.

Subjects whose condition worsens and require alternate or supplemental therapy for the treatment of head lice during the study will be discontinued, included in both the mITT and PP population analyses as treatment failures. Subjects who discontinue early for reasons other than treatment failure will be excluded from the PP population, but included in the mITT population. Last Observation Carried Forward (LOCF) will be used to impute any missing endpoints.

Efficacy analyses will be performed on both the per-protocol population and the mITT population. Safety analyses will be performed using the Safety population as defined.

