8. TABLES, LISTINGS AND FIGURES

Tables

- 1. Summary of Subject Enrollment and Disposition.
- 2. Summary of Subject Demographics at Screening (mITT population).
- 3. Summary of Subject Demographics at Screening (PP Population).
- 4. Summary of Medical History/Other Concomitant Illness at Screening.
- 5. Summary of Physical Exam Abnormalities.
- 6. The Difference in proportion of patients that are identified as cured on Study Day 15 (Visit 5) Treated with Ivermectin and Sklice (mITT population).
- 7. The Difference in proportion of patients that are identified as cured on Study Day 15 (Visit 5) Treated with Ivermectin and Sklice visit (PP population).
- 8. The Difference in proportion of patients that are identified as cured on Study Day 15 (Visit 5) Treated with Ivermectin Vs Placebo and Sklice Vs Placebo (mITT population).
- 9. The Difference in proportion of patients that are identified as cured on Study Day 15 (Visit 5) Treated with Ivermectin Vs Placebo and Sklice Vs Placebo (PP population).
- 10. Summary of Head Lice visual examination at each visit (mITT population).
- 11. Summary of Head Lice visual examination at each visit (PP Population).
- 12. The Difference in proportion of patients that are identified as cured on Study Day 2 (Visit 3) Treated with Ivermectin and Sklice (mITT population).
- 13. The Difference in proportion of patients that are identified as cured on Study Day 2 (Visit 3) Treated with Ivermectin and Sklice (PP population).
- 14. The Difference in proportion of patients that are identified as cured on Study Day 2 (Visit 3) Treated with Ivermectin Vs Placebo and Sklice Vs Placebo (mITT population).
- 15. The Difference in proportion of patients that are identified as cured on Study Day 2 (Visit 3) Treated with Ivermectin Vs Placebo and Sklice Vs Placebo (PP population).
- 16. Summary of self-assessment of itching and stinging/ burning sensations at each visit (mITT population).
- 17. Summary of self-assessment of itching and stinging/ burning sensations at each visit (PP population).
- 18. Summary of change of self-assessment of itching and stinging/ burning sensations from baseline at each visit (mITT population).
- 19. Summary of change of self-assessment of itching and stinging/ burning sensations from baseline at each visit (PP population).
- 20. Summary of local skin/scalp irritation assessment at each visit (mITT population).
- 21. Summary of local skin/scalp irritation assessment at each visit (PP population).

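### Local tolerability is tabulated only for mITT and PP, although the protocol treats it as a safety analysis and both documents assign safety analyses to the Safety population

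*SAP*

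**What the plan says.** The secondary objective in SAP 2 joins the two topics: "To demonstrate comparative safety and local tolerability of Ivermectin 0.5% lotion", against Sklice. In the protocol synopsis, the sentence "Analysis of tolerability will be based on scores of Stinging/Burning and Itching sensations" stands under the Safety Analysis heading.

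On populations, SAP 4 states "Safety analyses will be performed using the Safety population as defined", and Protocol 10.2 says the same. The Safety population "includes all subjects who were randomized and dispensed treatment". The mITT set adds two conditions: every entry criterion was met, and efficacy was evaluated at least once after treatment. PP narrows this further. It requires that the product was applied, that no deviation could have disturbed the efficacy assessment, and that the Day 15 visit fell in its window. SAP 4 adds: "Subjects who discontinue early for reasons other than treatment failure will be excluded from the PP population". Those subjects stay in mITT.

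SAP 5.3 then says "Tolerability analyses will be presented for mITT and PP populations". The output list in SAP 8 follows it. Tables 16-25 (self-assessed itching and stinging/burning, skin/scalp irritation, ocular irritation) and Figures 3-10 come in mITT and PP pairs, with no Safety version. SAP 6 anticipates no departure from the planned analyses, and no reason is given for the choice.

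**The concern.** mITT and PP are built for efficacy. Membership depends on eligibility, efficacy follow-up, compliance and, for PP, completion. Some of these conditions can be related to irritation itself, so a comparison of irritation within these sets may miss the subjects who matter most for it. That would tend to make the products look better tolerated than they were.

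The question is a real one here. Protocol 6.1.2 gives the test and reference lotions the same ivermectin strength but largely different inactive ingredients. Local tolerability is therefore not settled by the shared active ingredient.

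There is also a practical cost. The adverse event tables use the Safety population and the tolerability tables do not, so the two accounts of local reactions in the study report would have different denominators.

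**Working it through.** **1. The plan's own numbers.** Inputs from SAP 3.1: 280 mITT subjects (120:120:40), of whom about 90% qualify for PP.

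- 280 × 0.90 = 252; 120 × 0.90 = 108; 40 × 0.90 = 36. These match the stated PP numbers.
- Outside PP: 280 − 252 = 28, that is 12 + 12 + 4.

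The stated power was also reproduced, with cure rates of 67% and 27%. The check used 400,000 simulated trials, the SAP 5.2.2 interval in PP, and pooled continuity-corrected Z-tests in mITT (pooling is an assumption). Joint success was 81.5%, against the claimed minimum of 80%. The tolerability population does not enter that calculation.

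**2. Who is missing from which set.** Protocol 5.5.1 lets an adverse event end participation. It also discontinues subjects who newly meet an exclusion criterion that precludes continuing. Exclusion 4 cites an erythema score above 2 as an example, and the site scale stops at 3, so the worst grade could itself lead to withdrawal. Exclusions 3 to 5 cover sensitivity, scalp conditions, and eczema or atopic dermatitis. Protocol 13.2 allows departures from entry criteria with written sponsor approval, so treated subjects who breach a criterion can arise.

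Take three subjects in one active arm of 120 (assumed counts), with no other reactions in that arm and every other subject scored:

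| Case | Safety | mITT | PP |
|---|---|---|---|
| A. Eligible, scored with burning on Day 2, then withdraw for it | 3/120 = 2.5% | 3/120 = 2.5% | 0 events |
| B. Treated and scored with burning, later found ineligible | 3/120 = 2.5% | 0/117 | 0 events |
| C. Never return after treatment | 0/117 assessed | 0/117 | 0 events |

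PP loses the events in A and B. mITT loses them only in B. In C no set has a score, because lice checks and post-treatment tolerability scores are scheduled at the same visits.

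**3. How far PP could differ from Safety.** Suppose 5 of 108 PP subjects in an active arm have a reaction (assumed): 5/108 = 4.6%. Let k of the 12 excluded subjects also have one, so that the Safety rate is (5 + k)/120:

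- k = 0: 5/120 = 4.2%
- k = 3: 8/120 = 6.7%
- k = 6: 11/120 = 9.2%
- k = 12: 17/120 = 14.2%

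The last is an upper bound, not an expectation.

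**4. How far mITT could differ from Safety.** No loss rate is given. Taking 280 as randomized and dispensed, and assuming a loss of 0%, 2% or 5%:

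- 280 × 0 = 0
- 280 × 0.02 = 5.6
- 280 × 0.05 = 14

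Per active arm of 120 this is 0, 2.4 or 6. Only those who were scored (case B) would add data on moving to Safety.

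**The case against.** The strongest reply is that the harm is largely hypothetical. Every PP table has an mITT counterpart, and SAP 4 keeps early discontinuers in mITT. A reader might infer from SAP 5.3 that subjects who leave because of intolerance vanish from the tolerability tables altogether. The documents do not support that: case A stays in mITT, and withdrawal for a local reaction removes a subject from PP only. Treatment is also a single 10-minute application, so nobody can stop dosing for intolerance afterwards. They can only leave follow-up.

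Nor are local reactions hidden. Protocol 8.1.1 records signs or symptoms believed to be drug-related as adverse events, SAP 5.4 summarizes these in the Safety population, and SAP 7 provides listings for all subjects, including Listings 10-12 on tolerability. Eligibility is confirmed again before randomization (schedule of events, footnote 6), so breaches should be few.

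Finally, SAP 5.4 names adverse events as the safety variables, and tolerability has its own section outside it. The rule on safety analyses could be read as covering adverse events only.

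Most of this stands and limits the weight of the point. It does not remove it. The narrower reading of safety does not fit the synopsis, which puts tolerability under safety analysis. Not every graded score becomes an adverse event, and a listing is not a comparison between arms. Nothing in the plan explains why efficacy-selected sets should be the only ones used.

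**Conclusion.** The point holds as a minor, descriptive one. SAP 5.3 does not follow the population rule that the plan sets for safety analyses. The resulting selection is direct in PP (withdrawal for a local reaction) and narrower in mITT (treated and scored subjects who breach entry criteria, some of whom may be prone to irritation).

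Its size cannot be fixed from the documents. The 28 subjects outside PP are a planning figure for all causes, including deviations and missed visit windows. It would be wrong to read them as subjects lost to intolerance. The mITT-to-Safety gap is probably small, and the 2% and 5% used above are assumptions. Protocol 2.3.1 puts the listed reactions at under 1%, so below 120 × 0.01 = 1.2 subjects per active arm, and one or two subjects can matter for rare reactions. Those are reported reaction rates, however, not 0-3 scores in infested children, and cannot be carried over directly.

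Sample size, alpha, power and the primary conclusion are unaffected.

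**What to change.** In SAP 5.3, name the Safety population as the main set for tolerability, and add it to Tables 16-25 and Figures 3-10. Use all available assessments, analysed without imputation, and show the number assessed per arm and visit so that missing scores are visible. It is worth stating the no-imputation rule there: SAP 3.4.2 rules out imputing safety data, but the carry-forward sentence in SAP 4 is not limited to efficacy.

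The mITT and PP versions may stay as supportive; PP has some use because it requires that the product was applied. If the sponsor prefers mITT as the main set, SAP 5.3 should say why.

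The cost is a sentence and a population flag. Keeping all current versions adds five tables and four figures (ten tables and eight figures are now planned in pairs). Replacing the PP versions adds none.
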